5.3.2 Eligibility Criteria/Vulnerable Populations

The study population will include practice clinical and nonclinical NYULH staff and patients with uncontrolled HTN receiving care in the network of 10 safety-net practices in New York.

Patient Eligibility Criteria

Inclusion Criteria:

- Be fluent in English or Spanish
- Be age 18 years or older
- Receiving care at one of the 10 practices
- Have uncontrolled HTN documented in the EHR on at least two visits in the past year (defined as an average BP \geq 140/90 mmHg)
- Have been prescribed at least one anti-hypertensive medication and be non-adherent to their medications, defined as adherence $<80\%$ in the preceding 12 months, as determined by prescription orders obtained from the clinic EHR.

Exclusion Criteria:

- Being deemed unable to comply with the study protocol (either self-selected or by indicating during screening that s/he could not complete all requested tasks)
- Participation in other hypertension-related clinical trials
- Have significant psychiatric comorbidity or reports of substance abuse (as documented in the EHR)
- Plan to discontinue care at the practice within the next 15 months

Clinic and nonclinical staff Eligibility Criteria

Inclusion criteria:

- Primary care provider (MD/DO, NP), Nurse, Medical Assistant, or administrative staff employed at the participating practices and interacts with at least five patients with a diagnosis of HTN.

Exclusion criteria:

- Refuse to participate.

Control group eligibility criteria

Inclusion criteria:

- Patients who fit the inclusion criteria of the intervention group

Exclusion criteria:

- The same exclusion criteria of the intervention group will be applied to the control group
- Patients who refuse to participate in the evaluation

As ALTA grows and becomes standard-of-care, we anticipate that some patients may crossover from the control group to intervention group. The opposite will not occur because that is considered a withdrawal from the study. Our sample size for the control group can remain dynamic in that fashion, and we will recruit until the end of the evaluation period.

Vulnerable Populations

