Following the NIH Best Practices for mixed methods research, we will construct a joint display that integrates the qualitative themes with the quantitative data to create a composite measure of implementation fidelity based on the five dimensions outlined above. Should the data be divergent, we will assign higher credence to the qualitative data because it provides richer explanation about participants' behaviors. We will also explore the association between implementation fidelity and the clinical outcomes. This analysis will be accomplished with a multilevel MANOVA (unstructured covariance matrix across two time points: baseline and 12 months). The analysis will have one within person factor — Time (baseline and 12-month coded naturally as months (0 and 12)) and one primary between-

patient factor (Randomization Group dummy coded as 0 = UC and 1 = PF). We will use the composite measure of implementation fidelity to predict changes in BP control and medication adherence at 12 months. We will use a 3-level analytic model to accounting for nesting in the data (observations nested within subjects nested within practices). Multilevel modeling software (SAS, Version 9, PROC MIXED) will be used to compute full information maximum likelihood (FIML) estimates of the model parameters. The PROC MIXED procedure will use an error structure that allows for the possibility of group differences in (a) the error variances at 12 months; and (b) the serial correlations of the baseline with the 12 month outcomes. The primary test is the treatment X time interaction, and the resulting F-test will provide the primary "intent to treat" test of the hypothesis. If this is statistically significant at the two tailed $\alpha=.05$ level, for ease of interpretation, we will estimate and report the magnitude of the treatment effect, with 95% CI for fidelity. Covariates will be included as necessary in adjusted analyses. All tests will be 2-sided, 0.05 level tests.

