6.4.3.2 Secondary Objectives Analyses

The effect of PF on BP Control

Our main clinical outcome is the proportion of patients with adequate BP control (<140/90 mmHg) at 12 months in the implementation vs. UC phase. BP control will be treated as a dichotomous outcome variable in this analysis; any patients with missing follow-up BP data will be assumed to have inadequate BP control. To examine the difference in BP control rates between the implementation and UC phases, we will utilize a generalized linear mixed model (GLMM) to assess the PF effect. A Poisson regression model will be used to predict BP control specifying a fixed effect for time, a fixed effect for treatment and a time by treatment interaction. Random effects will be specified for person and practice to account for the clustered nature of the dataset (observations within person and people within practices). As a sensitivity analysis, we will also assess an alternate definition of BP control (< 130/80 mmHg) indicated by the new hypertension guidelines. In exploratory analyses, will examine the intervention effect on BP reduction at 12 months, treated as a continuous variable. An additional sensitivity analysis will be conducted using GLMM to evaluate the effect of PF on BP reduction. We will test the treatment X time interactions in a random effects linear regression model to determine the time-specific differences BP reduction attributable to PF at the end of the implementation phase.

Randomization of the stepped-wedge design should obviate the need for adjustment, but in the case of imbalanced in baseline covariates; these will be included as necessary in adjusted analyses. All tests will be two-sided with $\alpha=0.05$ for comparison between the implementation and UC phases. Maximum likelihood estimation of mixed-effects models will be used to account for missing data; in the context of a mixed-effects model, this is equivalent to an assumption of data that are missing at random (MAR); we will conduct sensitivity analyses assessing this assumption. We will also compare participants with and without missing values with respect to baseline and practice characteristics. If differential patterns emerge, we will consider the use of multiple imputation and/or inverse probability weighting to adjust for missing data. Analyses will be conducted using Stata, SAS, and R.

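### BP control has two treatment-by-time tests, a normal-errors PROC MIXED model labelled primary (6.4.3.1) and a Poisson GLMM (6.4.3.2), and the plan does not say which decides

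*Combined protocol and SAP*

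**What the plan says.** Section 6.4.3.1 (Primary Analyses), after describing the fidelity composite, turns to an exploratory look at fidelity and the clinical outcomes. The model is given as follows: "This analysis will be accomplished with a multilevel MANOVA (unstructured covariance matrix across two time points: baseline and 12 months". The software and estimator are stated: "Multilevel modeling software (SAS, Version 9, PROC MIXED) will be used to compute" the parameter estimates, by FIML. No link function or non-normal distribution is given. The outcomes are named: "We will use the composite measure of implementation fidelity to predict changes in BP control and medication adherence at 12 months". The same paragraph then gives the analysis confirmatory status: "The primary test is the treatment X time interaction, and the resulting F-test will provide the primary" intent-to-treat test of the hypothesis, at the two-sided 0.05 level. It promises a 95% confidence interval attached to fidelity, not to BP control or adherence.

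Section 6.4.3.2 says "BP control will be treated as a dichotomous outcome variable in this analysis". It uses a Poisson GLMM with time, treatment and their interaction, and random effects for person and practice. A patient without follow-up BP counts as not controlled. The section then gives PDC a GLMM of its own, and the association between fidelity and BP control a structural equation model.

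On entry, section 5.3.2 requires patients to "Have uncontrolled HTN documented in the EHR on at least two visits in the past year".

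**The concern.** BP control is called the major secondary outcome in 5.2.2 and the main clinical outcome in 6.4.3.2, and it is the only outcome with a power calculation (6.4.2). An analyst following the plan would produce two p-values for the practice-facilitation effect on it. They come from different error distributions, effect scales and missing-data rules. The one labelled primary sits in a paragraph introduced as exploratory. If the two fall on opposite sides of 0.05, nothing in the plan says which is reported as the result, and the choice would be made after the data are seen. PDC has the same problem in milder form.

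**Working it through.** **1. The two specifications side by side**

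| | 6.4.3.1 | 6.4.3.2 |
|---|---|---|
| Model | Multilevel MANOVA in PROC MIXED (normal errors) | Poisson GLMM |
| BP control enters as | One of two outcomes, baseline and 12 months | Dichotomous outcome |
| Tested term | Treatment × time | Treatment × time |
| Effect scale | Additive (difference of differences) | Ratio of ratios |
| Missing follow-up BP | FIML | Counted as not controlled; the section later also invokes maximum likelihood under MAR |
| Status | Primary intent-to-treat test | Test of the facilitation effect on the main clinical outcome |

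PDC appears in the 6.4.3.1 model, has its own GLMM in 6.4.3.2, and is listed again for GLMM testing in 6.4.3.3.

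**2. The plan's own figure.** Section 6.4.2 states at least 80% power for a 15-point difference and over 90% for 20 points, with 10 sites, 700 patients and ICC 0.01 to 0.05. It does not say which of the two tests this describes. The closed-form stepped-wedge variance for cross-sectional data (29% under usual care, two sites at each of five steps, six periods) gives the following:
- With 700/(10 × 6) = 11.7 patients per site-period, power for 15 points is 78%, 72% and 69% at ICC 0.01, 0.03 and 0.05. For 20 points it is 95%, 92% and 90%.
- With 35 per site-period, power for 15 points is 98% to 99%.

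The number per site-period is not stated, so the figure is neither confirmed nor refuted. The present point does not depend on it.

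**3. Do the two tests ask the same question?** Let b be the baseline and f the 12-month control rate. The additive null is (f_PF − b_PF) − (f_UC − b_UC) = 0. The ratio null is (f_PF/b_PF)/(f_UC/b_UC) = 1. They coincide only when baselines are equal or time has no effect. For example, with UC 10% → 20% and PF 20% → 40%, the additive contrast is 20 − 10 = 10 points, while the ratio contrast is 2.0/2.0 = 1.0.

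A simulation shows the size. Assumptions: 350 per group (700/2), no clustering, baseline and follow-up drawn independently, 4,000 replicates, two-sided 0.05. All baseline rates are assumed, because the documents give none.

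| UC; PF | Additive | Log-ratio, binomial variance | Log-ratio, Poisson variance |
|---|---|---|---|
| 10→20%; 20→40% (ratio null true) | 65% | 5% | 3% |
| 10→25%; 20→35% (additive null true) | 5% | 35% | 28% |
| 10→29%; 10→44% | 94% | 39% | 33% |
| 10→29%; 10→29% (no effect) | 4.7% | 4.3% | 2.9% |

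The first two rows differ because the nulls differ. The third has equal baselines, so the nulls coincide and the gap is one of power.

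**4. Low baseline control.** The variance of a binary outcome is p(1 − p): 0.01 × 0.99 = 0.0099; 0.05 × 0.95 = 0.0475; 0.10 × 0.90 = 0.09. At 12 months it is 0.29 × 0.71 = 0.206 and 0.49 × 0.51 = 0.250, taking the 29% usual-care rate in 6.4.2 plus the planned 20 points. The 29% variance is thus about 21, 4.3 or 2.3 times the baseline variance at 1%, 5% or 10%.
- In 6.4.3.1, the baseline-to-12-month correlation would rest on few controlled patients: 3.5, 17.5 or 35 of 350.
- In 6.4.3.2, the log of a baseline proportion has variance (1 − p)/(np). With n = 350 this is 99/350 = 0.283 at 1%, 19/350 = 0.054 at 5% and 9/350 = 0.026 at 10%, against 2.45/350 = 0.007 at 29%. The ratio interaction becomes imprecise as baseline control falls.

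**5. Poisson variance.** Without robust errors, which are not mentioned, the Poisson standard error is too large for a binary outcome by 1/√(1 − p): 1/√0.71 = 1.19 at 29% and 1/√0.51 = 1.40 at 49%. The 6.4.3.2 model is therefore not a clean reference either.

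**The case against.** The best defence is that 6.4.3.1 concerns fidelity. Its paragraph opens as an exploration and ends with an interval for fidelity, while 6.4.3.2 plainly assigns the GLMM to the facilitation effect on BP control. On that reading, the word primary belongs to fidelity or to the lead contrast of an exploratory model. What stands is that 6.4.3.2 is the natural home for the BP-control test and that the dependent variable in 6.4.3.1 is unclear. The defence does not remove the conflict, because the paragraph names BP control and adherence as what is predicted and then declares a primary intent-to-treat test at 0.05. Taking fidelity as the outcome does not rescue it: ALTA is not implemented during usual care (6.1.1), so fidelity has no patient-level value at month 0.

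A reader might infer more than the documents support:
- **That baseline control is essentially 0% and the covariance singular.** Eligibility uses an average over at least two visits in the past year. Baseline control uses the mean of the last two readings in the pre-intervention period (5.2.2). These readings can differ, and no baseline rate is given. The unstructured covariance already allows unequal variances.
- **That PROC MIXED will fail to converge.** This is possible, but nothing shows it.
- **That normal errors make the test invalid.** With equal baselines and no effect, the additive test rejected 4.7% of the time. A difference in proportions is also the scale on which 6.4.2 plans the trial.
- **That only PROC MIXED suffers from a low baseline.** The log-scale interaction in 6.4.3.2 is affected too.

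**Conclusion.** The point holds as a conflict of specification. As written, the plan gives one hypothesis about BP control two tests, with different scales and missing-data rules, and attaches the primary label to the one in the exploratory paragraph. Under assumed rates the choice can matter a great deal (94% against 39% rejection in the equal-baseline case), but those figures come from an unclustered parallel-group simplification and illustrate potential disagreement only. They do not predict this trial's power. A low baseline control rate is a reasonable inference from eligibility, and it is a reason not to use baseline control as an outcome in either model. The finding does not rest on it: the text of 6.4.3.1 and 6.4.3.2 suffices.

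**What to change.** In 6.4.3.1, delete the sentence that makes the treatment-by-time F-test the primary intent-to-treat test, together with the confidence interval for fidelity. Remove treatment-effect testing of BP control and PDC from PROC MIXED.

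In 6.4.3.2, name one deciding model for BP control: a binary-outcome GLMM of follow-up control, or Poisson with robust errors. Include phase, calendar period and practice, with baseline SBP as a covariate. State one effect scale and one missing-data rule. Say which readings supply the outcome in the usual-care phase, since 6.1.1 collects baseline measures in that phase. Name the 6.4.3.2 GLMM as the deciding model for PDC and align 6.4.3.3 with it.

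Keep the association between fidelity and outcomes as a separate exploratory analysis on implementation-phase data only. Use one method, reconciling 6.4.3.1 with the structural equation model in 6.4.3.2. Do not add fidelity to the treatment-effect model, because it is undefined under usual care.

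The cost is SAP rewording and one fewer test of BP control.

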5.1 General Design

Using a stepped-wedge cluster randomized control trial design, this study will evaluate the effect of a tailored PF strategy on the implementation of Advancing Long-term Improvements in Hypertension Outcomes through a Team-based Care Approach (ALTA), our systems-level approach to improving medication adherence and BP control, among patients with uncontrolled HTN receiving care in 10 safety-net practices in New York.

Using a mixed-methods approach, this study will be conducted in two phases: (1) a pre-implementation phase where we will refine the PF strategy, based on the Consolidated Framework for Implementation Research (CFIR) to facilitate implementation of ALTA at the practices and (2) an implementation phase, guided by Proctor's Implementation Outcomes Framework (IOF). The primary aim of the implementation phase is to evaluate, in a stepped-wedge cluster randomized trial, the level of implementation fidelity (e.g., degree to which a program is delivered, as intended) of ALTA because of the tailored PF strategies. The secondary aims are to compare the effects of PF versus usual care (UC) on BP control and medication adherence in 10 safety-net primary care practices and patients with uncontrolled HTN who are non-adherent to their antihypertensive medications. We will also explore the potential moderating factors at the practice and individual levels (e.g., organizational capacity to change, evidence-based practice attitudes) that influence level of implementation fidelity of ALTA at the practices. We will also explore the impact of ALTA on the patient-provider relationship (i.e., relationship commitment, patient-provider trust, and patient anxiety in the interaction), and determine whether any changes to the relationship also affect patients' BP control and medication adherence.

As shown in Figure 1, each participating practice will start with the UC phase and are block-randomized into four waves, with two sites per wave. The UC phase will be followed by the pre-implementation phase of 6 months, during which facilitators will conduct a practice evaluation (e.g., workflow analysis, environmental scan) based on CFIR, refine the PF strategies that will be used in the implementation phase, and train staff in the ALTA model. Following this period, sites will implement ALTA with the assistance of the facilitator for 12 months, with a 3-month follow-up period for outcome assessment.

Figure 1. Stepped wedge design of ALTA implementation

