5.1.2 Number of Study Sites

The study will be conducted at the network of 10 safety-net practices in New York.

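### With 10 randomised practices, the maximum likelihood mixed models name no practice-by-period effect and no small-sample reference, so the 0.05 level is not assured and is probably exceeded in the linear models

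*Combined protocol and SAP*

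**What the plan says.** Section 5.1.2: "The study will be conducted at the network of 10 safety-net practices in New York". Section 5.1 randomises practices, not patients, in a stepped wedge; they are "block-randomized into four waves, with two sites per wave". That places eight practices, whereas Figure 1 shows five cohorts, which at two each would place all ten.

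Section 6.4.3.1 specifies a three-level model (observations, patients, practices) in PROC MIXED with "full information maximum likelihood (FIML) estimates of the model parameters". The test is treatment by time, and "the resulting F-test will provide the primary" intention-to-treat test. No denominator degrees of freedom are given. The section ends: "All tests will be 2-sided, 0.05 level tests".

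Section 6.4.3.2 fits BP control, a yes/no outcome, with a Poisson GLMM that has random effects for person and practice. Tests are two-sided at 0.05 "for comparison between the implementation and UC phases". The section adds: "Maximum likelihood estimation of mixed-effects models will be used to account for missing data". PDC gets a similar maximum likelihood model, with rank or beta regression as possible alternatives. Section 6.4.3.3 repeats the structure for the tertiary outcomes.

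No section names REML, Kenward-Roger, Satterthwaite, a t reference, a permutation test or any other small-sample method, and none names a random effect for practice by period.

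**The concern.** The treatment effect is judged against variation between practices, and only 10 practices inform that variation. Two gaps matter.

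- **Reference distribution.** With so few clusters, a normal reference treats an uncertain standard error as known.
- **Practice-by-period variation.** A single practice intercept assumes that two patients in one practice are equally alike whether they were seen in the same quarter or years apart. Figure 1 spreads the rollout over four years. If practices drift, part of that drift is counted as precision about treatment.

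Both gaps make intervals too narrow in linear models. The choice also affects the sample size claim, since a small-sample reference costs power. If the choice is left until the data are seen, it can decide whether a borderline result is called significant.

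**Working it through.** **Inputs from the documents.** 10 practices; 700 patients, 70 per practice; ICC 0.01 to 0.05; differences of 15 and 20 points; 29% control under usual care in the earlier trial (section 6.4.2); two-sided 0.05.

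**Assumptions.** Five waves of two; six periods with no transition gap; 12, 14 or 24 patients per practice-period; cluster autocorrelation (CAC, the share of practice-level correlation that persists over time) from 0.5 to 1. The documents give no number of periods, cell size or CAC.

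**1. The plan's power figure.** The Hussey-Hughes variance is

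Var = I·s²(s² + T·τ²) / [(IU − W)s² + (U² + ITU − TW − IV)τ²].

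Here I = 10, T = 6, U = 30, W = 220, V = 110, so the two brackets are 80 and 280. Mean binomial variance at 29% and 44% is (0.2059 + 0.2464)/2 = 0.2262. With ICC 0.05 and 14 per cell, τ² = 0.01131 and s² = 0.95 × 0.2262/14 = 0.01535. The standard error is 0.0539, and 0.15/0.0539 = 2.78.

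- z reference: Φ(2.78 − 1.96) = 79.5%. At ICC 0.01 it is 85.5%.
- 20 points, z reference: 98.0% (ICC 0.01) and 95.9% (ICC 0.05).

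This is close to the stated figures but does not reproduce them firmly. Fourteen per cell implies 10 × 6 × 14 = 840 observations. Spreading 70 patients over six periods (11.7 per cell) gives 79.6% to 72.7%. Two observations per patient (23.3 per cell) gives 96.5% to 94.0%.

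**2. Type I error in the stepped wedge.** Simulation under no effect, 29% control, practice random intercept only; 2,000 runs at 12 per cell and 1,200 at 24 (Monte Carlo standard error at 5%: √(0.05 × 0.95/2000) = 0.5 and 0.6 points).

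| Per cell | ICC | CAC | Linear ML, z | Linear REML, z | Linear REML, t(8) | Poisson GLMM ML, z |
|---|---|---|---|---|---|---|
| 12 | 0.01 | 1 | 6.6% | 6.3% | 2.9% | 3.6% |
| 12 | 0.01 | 0.8 | 6.5% | 6.2% | 2.3% | 2.8% |
| 12 | 0.05 | 1 | 6.4% | 6.0% | 3.0% | 3.6% |
| 12 | 0.05 | 0.8 | 7.7% | 7.2% | 3.0% | 3.9% |
| 12 | 0.05 | 0.5 | 9.2% | 8.5% | 5.2% | 5.6% |
| 24 | 0.05 | 1 | 6.6% | 6.4% | 2.7% | 2.9% |
| 24 | 0.05 | 0.8 | 8.8% | 8.3% | 3.8% | 4.4% |
| 24 | 0.05 | 0.5 | 12.9% | 12.8% | 7.1% | 7.2% |

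A second simulation of the linear model (ML, z) gave 6.6-7.0% at constant correlation and 8.1-8.7% at CAC 0.8 to 0.5.

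Switching from ML to REML hardly moves the z columns; the reference distribution does. The last row shows that t(8) alone does not cure an omitted practice-by-period term. The Poisson column is low because the model takes the variance as p rather than p(1 − p). At 29% that inflates the standard error by about √(1/0.71) = 1.19. The Poisson fit used one observation per patient and no person effect.

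**3. The 6.4.3.1 contrast read literally.** Take two groups of five practices, 70 patients each, two time points and a practice intercept only. A stable practice effect cancels in the change score. Practice-by-time variance does not: it contributes b = 2·ICC·(1 − CAC), against patient-level w = 2(1 − ICC)(1 − ρ). Assume half the residual variance is stable within patient (ρ = 0.5). The variance is then understated by 1 + 69·b/(b + w):

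- ICC 0.01, CAC 0.8: b = 0.004, w = 0.99, factor 1.28, error 2[1 − Φ(1.96/√1.28)] = 8.3% (simulated 8.3%).
- ICC 0.05, CAC 0.8: factor 2.42, error 20.8% (simulated 21.5%).
- ICC 0.05, CAC 0.5: factor 4.45, error 35.3% (simulated 35.6%); with ρ = 0 it is 23.9%.
- No practice-by-time variance: simulated 5.1-5.2%.

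Adding the practice-by-time term but keeping ML and z still gives 10.8% and 11.8% in the two ICC 0.05 cases. A practice-level t-test with 8 df gives 4.9-5.3% throughout.

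**4. Power under t(8).** Critical value 2.306, noncentral t, 14 per cell. For 15 points power is 75.3% at ICC 0.01 and 68.5% at ICC 0.05. For 20 points it is 93.8% and 89.8%.

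**The case against.** The strongest reply is that a reader might infer more than the documents support, in four ways.

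- **That every test is affected.** Not so. Dose and responsiveness use weighted ANOVA, indirect effects use bootstrap intervals, and PDC may move to rank or beta regression.
- **That the BP control test is too liberal.** As written, the Poisson GLMM is conservative in most scenarios. This stands. It is no safeguard, however: the low error comes from a wrong variance. If an analyst repaired that with practice-clustered robust errors, which the plan does not mention, simulation gave 11.5-13.5% with z.
- **That the plan uses Wald z tests, with error of 8.6% (1.96 against t(8)) or 11.6% (a parallel comparison of five practices with five).** Section 6.4.3.1 names an F-test with unstated degrees of freedom, and nothing in the plan mentions a Wald z. Neither figure describes a stepped wedge with within-practice comparison.
- **That maximum likelihood is the culprit.** In the stepped wedge, REML with z gives nearly the same error.

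It is also fair to say that decaying correlation is an assumption, that 6-7% is a modest excess, and that the primary outcome is a mixed-methods fidelity composite, so these tests concern mainly secondary and tertiary outcomes. What survives is that the plan in effect fixes the autocorrelation at 1 and leaves the reference distribution open.

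**Conclusion.** The point holds in limited form; it should be fixed, with moderate confidence. With 10 practices, the mixed models in 6.4.3.1 to 6.4.3.3 do not secure the 0.05 level.

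- **Linear-type models (PDC, continuous BP, continuous tertiary outcomes):** about 6-7% at constant correlation; about 8-13% at ICC 0.05 with CAC 0.8 to 0.5. At ICC 0.01 and CAC 0.8 it stays at 6.5%. Section 6.4.3.3 assigns a Poisson model to relationship commitment although it is continuous, so the linear figures apply to it only if it is fitted as linear.
- **The 6.4.3.1 contrast:** near 5% without practice-by-time variance, and far higher with it.
- **BP control as written:** about 3-4%, and 6-7% only at CAC 0.5. Its level is not 5% either.

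These figures assume a normal-type reference, five waves of two, and cell sizes the documents do not give. The exact excess cannot be fixed from the documents.

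**What to change.** 1. Add a practice-by-period random effect to every mixed model, linear or not.
2. Fit linear models by REML with Kenward-Roger degrees of freedom. REML keeps the likelihood-based missing-at-random handling.
3. For BP control, use a model suited to a binary outcome with a t(8)-type reference and state the effect scale. Alternatively, use a permutation test over the actual wave allocation. Five waves of two give 10!/(2!)⁵ = 113,400 allocations, but section 5.1 says four waves and must first be reconciled with Figure 1.
4. State the denominator degrees of freedom for the 6.4.3.1 F-test.
5. Restate power under the chosen reference, giving periods, cell size and usual-care rate.

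**Cost.** This is analysis-plan wording, with no new data, and should be settled before any comparison by treatment phase. Intervals widen, t(8) can be conservative (down to 2.3% in the table), and a practice-by-period variance is poorly estimated from 10 practices. At 14 per cell, power for 15 points falls from 85.5% to 75.3% (ICC 0.01) and from 79.5% to 68.5% (ICC 0.05), below the claimed 80%. With 23.3 per cell it would be 90.8% and 86.8%, so the claim depends on an unstated input. These power figures do not include practice-by-period variance, which would lower them further.

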6.4.2 Sample Size Considerations

Power calculations are based on the clinical outcome of BP control using our prior work implementing the ALTA model in a community-based clinic. In the former trial, we found a significant improvement in attainment of BP control at 6 months among patients randomized to the intervention group compared to the UC group (51% vs. 29%, $p=.03$). We expect a similar group difference of a 20% increase in BP control between the implementation and UC phases in the current study. Calculations of achieved power were estimated with a stepped-wedge design using Power Analysis and Sample Size (PASS) software program. The power calculations show that we can recruit 10 sites and 700 patients and have at least 80% power to detect a more conservative 15% difference in BP control between the UC and implementation phases for intraclass correlation coefficients (ICCs) ranging from 0.01 to 0.05. Using our original estimate of a 20% difference in BP control, we would have over 90% power to detect a difference between the UC and implementation phases with 10 sites and 700 patients.

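### The primary analysis provides for a fidelity effect estimate and 95% CI only after a significant test, so a non-significant primary result would be left with a p-value alone

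*Combined protocol and SAP*

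**What the plan says.** In Section 6.4.3.1 (Primary Analyses), the last paragraph describes a three-level mixed model, calls the treatment by time interaction the primary intent-to-treat test, and continues: "If this is statistically significant at the two tailed" 0.05 level, "for ease of interpretation, we will estimate and report the magnitude of the treatment effect, with 95% CI for fidelity". The same paragraph adds "All tests will be 2-sided, 0.05 level tests". There is no sentence on what is estimated or reported when the test is not significant.

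Three other places might have filled the gap, and none does:

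- The same paragraph says that the mixed-model software "will be used to compute full information maximum likelihood (FIML) estimates of the model parameters". This describes how the model is fitted. It does not promise to report an effect.
- Earlier in Section 6.4.3.1, analysis-of-variance models for dose and responsiveness compare the practices with each other. They do not compare practice facilitation with usual care.
- Section 6.4.3.5 promises descriptive summaries of baseline characteristics and outcomes. These are not a treatment effect with an interval.

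On power, Section 6.4.2 says "Power calculations are based on the clinical outcome of BP control", which is a secondary outcome. No power is given for fidelity.

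**The concern.** Fidelity is the primary outcome (Section 5.2.1), and how far facilitation raises it is the question that the implementation phase is meant to answer. The condition covers both estimating and reporting. If the test is not significant, the written plan yields no magnitude and no range of plausible values. A reader could not tell a trial showing that facilitation makes little difference from one whose 10 practices gave too little precision to say. The interval makes that distinction, and a non-significant result is where it is most needed.

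There is also a selection effect. If estimates appear only when they pass a significance threshold, those that appear are larger on average than the truth. How much larger depends on power.

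**Working it through.** **The plan's own figure.** The only stated power is for BP control with 10 sites and 700 patients at ICCs of 0.01 to 0.05: at least 80% for a 15-point difference and over 90% for a 20-point difference (Section 6.4.2). I approximated this with the Hussey-Hughes stepped-wedge formula. Assumptions: five waves of two sites (the cohorts in Figure 1), six periods and a usual-care rate of 29%.

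- With 70/6 patients per site-period and the average-rate variance, 15 points gives 78.6% (ICC 0.01) to 71.6% (ICC 0.05). Twenty points gives 95.2% to 91.5%.
- With 70/5 per site-period and the usual-care variance, 15 points gives 88.5% to 83.1%.

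The plan does not give the settings needed to choose between these, so the 80% figure is neither confirmed nor refuted. The point does not depend on it, because it concerns a different outcome. For fidelity, power has to be treated as an assumption and shown over a range.

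**Set-up.** Let δ be the true effect divided by its standard error, Z ~ N(δ, 1) the estimate divided by its standard error, and c = 1.96. The rule reports only if |Z| > c.

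- Power: π = Φ(δ − c) + Φ(−δ − c)
- Chance of no estimate: 1 − π
- Mean reported estimate over the true effect (signed): R = 1 + [φ(c − δ) − φ(c + δ)] / (δπ)
- Coverage of the reported interval, for 0 < δ < 3.92: C = [0.975 − Φ(c − δ)] / π

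**Numbers put in.**

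- π = 0.80: δ = 2.802, R = 1 + 0.280 / (2.802 × 0.80) = 1.125, C = (0.975 − 0.200) / 0.80 = 0.969.
- π = 0.50: δ = 1.960, R = 1 + (0.3989 − 0.0002) / (1.960 × 0.50) = 1.407, C = (0.975 − 0.500) / 0.50 = 0.950.

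| Assumed power | No estimate | R | C |
|---|---|---|---|
| 90% | 10% | 1.060 | 97.2% |
| 80% | 20% | 1.125 | 96.9% |
| 50% | 50% | 1.407 | 95.0% |
| 20% | 80% | 2.236 | 87.0% |

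Because Φ(c − δ) is close to 1 − π in this range, C is about 1 − 0.025/π. This equals 0.95 at π = 0.50, so coverage drops below 95% only when power is below about one half.

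**Check on small numbers of clusters.** With a t reference on 8 degrees of freedom (assumed from 10 sites), the pattern is the same. About 78% power gives R = 1.11 and coverage 96.0%; about 49% gives 1.32 and 94.7%; about 21% gives 1.92 and 87.6%.

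**Reporting always.** Simulation at 20%, 50% and 80% power gave a mean ratio of 1.00 and coverage of 95.0% over all trials, and every trial has an estimate.

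**The case against.** The strongest reply is that the sentence says if, not only if, and gives ease of interpretation as its reason. It can be read as a follow-up that turns an interaction F-test into a readable magnitude. The model parameters are estimated in any case, and nowhere does the plan say that a null estimate will be withheld. That is fair about intent. It does not supply a commitment to report, and the plan should match the intent.

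A reader might also infer that the condition makes this trial's published effect exaggerated and its interval untrustworthy. The documents do not support that. If the test is significant, the same estimate and interval are reported with or without the condition. The ratios in the table describe averages over significant results in repeated trials, and removing the condition would not change them. Coverage among reported intervals is at or slightly above 95% from about 50% power upward. The 20% row is a scenario, since no fidelity power is stated.

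Nor can one infer that a null result is likely. Section 6.1.1 says that ALTA is not implemented during usual care, and the adherence domain is the share of components fully implemented. A contrast with usual care on that domain could be large by design. What stands is that the chance of a null result is unknown.

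Finally, a reader might extend the point to BP control, medication adherence (PDC) and the tertiary outcomes. Sections 6.4.3.2 and 6.4.3.3 set no such condition, so there is nothing there to correct.

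One further objection stands in full. The paragraph opens with the association between fidelity and the clinical outcomes, with fidelity as predictor, and then speaks of an effect for fidelity. The outcome of the primary test is therefore not clearly named, and removing the condition without naming it would leave the statistician unsure what to report.

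**Conclusion.** The point holds as a reporting gap in the primary analysis. If the primary test is not significant, the written plan provides no effect estimate or interval for fidelity. The chance of this is one minus power: 10%, 20% and 50% at assumed powers of 90%, 80% and 50%. That arithmetic needs no distributional model, only a power figure, which the plan does not give for fidelity. The selection of larger estimates is real but secondary: about 6% on average at 90% power, 12.5% at 80% and 41% at 50%, under a normal approximation that may not suit a mixed-methods composite. The defect should be corrected because it affects the primary outcome and costs almost nothing. It does not undermine the trial or bias the estimator.

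**What to change.** In Section 6.4.3.1 only, replace the conditional sentence with:

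*The magnitude of the treatment × time effect on implementation fidelity, with its 95% CI, will be estimated and reported regardless of the statistical significance of the test.*

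This names fidelity as the outcome. The sponsor should confirm that this is the outcome of the named F-test, and set the model in which fidelity predicts BP control and adherence apart from it. No change is needed for BP control, PDC or the tertiary outcomes. The cost is one sentence in the analysis plan, with no added data, visits or patients.
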